6.6.3 Adverse Events

All Adverse Events (AE) will be graded by the investigators using CTCAE v4.03. The AE verbatim descriptions (investigator terms from the CRF) will be classified into standardized medical

terminology using the Medical Dictionary for Regulatory Activities (MedDRA). Adverse events will be coded to the MedDRA (Version 22.0) lower level term (LLT) closest to the verbatim term. The linked MedDRA preferred term (PT) and primary system organ class (SOC) are also captured in the database.

The incidence of TEAEs will be summarized descriptively. A TEAE is defined as an AE that emerged during treatment or up to 30 days (90 days for SAEs and /or events of clinical interest) following last dose of study drug, having been absent at pretreatment (Baseline) or

- Reemerged during treatment or up to 30 days (90 days for SAEs and /or events of clinical interest) following last dose of study drug, having been present at pretreatment (Baseline) but stopped before treatment, or
- Worsened in severity during treatment or up to 30 days (90 days for SAEs and /or events of clinical interest) following last dose of study drug relative to the pretreatment state, when the AE was continuing.

Per protocol amendment 1, Events of clinical interest (ECI) for this trial include: an elevated aspartate aminotransferase (AST) or alanine aminotransferase (ALT) lab value that is greater than or equal to $3 \times$ ULN and an elevated total bilirubin lab value that is greater than or equal to $2 \times$ ULN and, at the same time, an alkaline phosphatase lab value that is less than $2 \times$ ULN, as determined by way of protocol-specified laboratory testing or unscheduled laboratory testing.

We used the following AE PT terms to identify ECI above:

- ALT increased
- AST increased
- Blood bilirubin increased
- Blood alkaline phosphatase increased

Only those AEs that are treatment emergent will be included in summary tables. All AEs, treatment emergent or otherwise, will be presented in subject data listings.

An overview table, including the incidence of and the number of subjects with TEAEs, TEAEs with grade 3 or above, serious adverse events (SAEs), deaths, and TEAEs that led to death, treatment discontinuation, dose reduction, or dose interruption will be provided.

The incidence of TEAEs will be reported as the number (percentage) of subjects with TEAEs by SOC and PT. A subject will be counted only once within a SOC and PT, even if the subject experienced more than one TEAE within a specific SOC and PT. TEAEs by preferred term, and CTCAE Grade will be summarized in descending frequency order.

The number (percentage) of subjects with treatment-related TEAEs including Eribulin, Pembrolizumab, both Eribulin and Pembrolizumab will be summarized by SOC and PT. Treatment-related TEAEs include those events considered by the investigator to be possibly or probably related to study treatment or with missing assessment of the causal relationship.

The number (percentage) of subjects with TEAEs leading to death, TEAEs with grade 3 or above, SAEs, TEAEs leading to discontinuation from study drugs, TEAEs leading to study drug dose reduction of eribulin and TEAEs leading to study drug interruption of study drugs will be summarized by MedDRA SOC and PT in separate tables. Separate subject data listings of all AEs, all AEs leading to death, treatment-related AE, grade 3 or above AEs, SAEs, and AEs leading to discontinuation from study drug will be provided.

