9.3.1 Inclusion Criteria

Subjects must meet all of the following criteria to be included in the study.

1. Females or males, aged ≥ 18 years at the time of signing the informed consent form (ICF)
2. Metastatic triple-negative breast cancer (confirmed from most recent tissue sample) meeting the following criteria:
 - a. Estrogen receptor (ER) and progesterone receptor negative (a tumor is ER and/or progesterone receptor positive if at least 1% of the cells examined have estrogen and/or progesterone receptors) and human epidermal growth factor receptor 2 (HER2) -negative (defined as immunohistochemistry (IHC) $<2+$ or fluorescence in situ hybridization (FISH) negative).
 - b. Previously treated with 0 to 2 lines of systemic anticancer therapy (cytotoxic or targeted anticancer agents) in the metastatic setting. Hormonal therapy and bone metastases treatment (eg, bisphosphonates, denosumab, etc) are not considered forms of systemic anticancer therapy.
3. Presence of measurable disease meeting the following criteria:
 - a. At least 1 lesion of ≥ 10 mm in long axis diameter for nonlymph nodes or ≥ 15 mm in short axis diameter for lymph nodes that is serially measurable according to RECIST 1.1 using either computerized tomography or magnetic resonance imaging or panoramic and close-up color photography.
 - b. Lesions that have had radiotherapy must show subsequent radiographic evidence of increased size to be deemed a target lesion.
4. Life expectancy of ≥ 3 months
5. Eastern Cooperative Oncology Group (ECOG) performance status (PS) of 0 or 1
6. Adequate renal function as evidenced by serum creatinine ≤ 1.5 mg/dL or calculated creatinine clearance ≥ 50 mL/minute according to the Cockcroft and Gault formula
7. Adequate bone marrow function, defined as:
 - a. Absolute neutrophil count (ANC) $\geq 1.5 \times 10^9/L$
 - b. Hemoglobin (Hb) ≥ 10.0 g/dL (can be corrected by growth factor or transfusion)
 - c. Platelet count $\geq 100 \times 10^9/L$
8. Adequate liver function, defined as:
 - a. Total bilirubin $\leq 1.5 \times$ upper limit of normal (ULN)

- b. Alkaline phosphatase (ALP), alanine aminotransferase (ALT), and aspartate aminotransferase (AST) $\leq 3 \times$ ULN unless there are bone metastases, in which case liver specific alkaline phosphatase must be separated from the total and used to assess the liver function instead of the total alkaline phosphatase. ALT and AST $\leq 5 \times$ ULN if subject has liver metastases

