Abnormal laboratory values should not be listed as separate AEs if they are considered to be part of the clinical syndrome that is being reported as an AE. It is the responsibility of the investigator to review all laboratory findings in all subjects and determine whether they constitute an AE. Medical and scientific judgment should be exercised in deciding whether an isolated laboratory abnormality should be classified as an AE. Any laboratory abnormality considered to constitute an AE should be reported on the Adverse Event CRF.

All AEs must be followed for 30 days after the subject's last dose, or until resolution, or the start of new anticancer therapy, whichever comes first. SAEs must be followed for 90 days and ECIs for 30 days (see [Section 9.5.1.6.2](#)) after the last dose of study drug or, if the subject initiates new anticancer therapy, for 30 days following the last dose of study drug, whichever is earlier. However, treatment-emergent peripheral neuropathy of any grade will be followed until return to baseline or until another anticancer therapy is started, whichever occurs first. All SAEs should be followed to resolution or, if resolution is unlikely, to stabilization.

A treatment-emergent adverse event (TEAE) is defined as an AE that emerges during treatment, having been absent at pretreatment (Baseline), or:

- Reemerges during treatment, having been present at pretreatment (Baseline) but stopped before treatment, or
- Worsens in severity during treatment relative to the pretreatment state, when the AE is continuous.

Disease progression is a study endpoint and should be captured in the CRF as per the guidelines for reporting disease progression.

Every effort must be made by the investigator to categorize each AE according to its severity and its relationship to the study treatment.

Assessing Severity of Adverse Events

AEs will be graded on a 5-point scale according to Common Terminology Criteria for Adverse Events ([CTCAE v4.03]; see [Appendix 6](#); also available from: <http://www.hrc.govt.nz/sites/default/files/CTCAE%20manual%20-%20DMCC.pdf>). Investigators will report CTCAE grades for all AEs (for both increasing and decreasing severity).

Assessing Relationship to Study Treatment

Items to be considered when assessing the relationship of an AE to the study treatment are:

- Temporal relationship of the onset of the event to the initiation of the study treatment

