- a: End of Treatment assessments for all subjects will be collected within 30 days of the last dose of study drug. Subjects with SAEs and/or ECIs at the time of End of Treatment will be followed for 90 days after the last dose of study drug or, if the subject initiates new anticancer therapy, for 30 days following the last dose of study drug, whichever is earlier. However, treatment-emergent peripheral neuropathy of any grade will be followed until resolution or until another anticancer therapy is started, whichever occurs first. All SAEs should be followed to resolution or, if resolution is unlikely, to stabilization.
- b: Demography information includes date of birth (or age), sex, and race/ethnicity.
- c: TNM staging at the time of diagnosis should be recorded in the eCRF.
- d: A serum (6-mL blood sample will be collected) or urine β -hCG test will be performed at the Screening Visit for premenopausal women and postmenopausal women who have been amenorrheic for less than 12 months. If a negative screening pregnancy test is obtained more than 72 hours before the planned first dose of pembrolizumab and eribulin mesylate, a separate serum or urine sample must be obtained and tested at the Baseline Visit assessment on C1D1.
- e: Pharmacokinetic blood samples will be collected only for eribulin mesylate PK analysis. Time points for PK sample collections are as follows: For all Phase 1b subjects, PK samples will be collected on C1D1 at predose (0 hour), 15, 30 minutes and 1, 2, 4, 8, 24, 48, 72, 96, 120, and 144 hours after the study drug infusion. For Phase 2 subjects, PK samples will be collected, if feasible, on C1D1 (at the end of the infusion, 0.5 to 6 hours and 24 to 120 hours after study drug infusion) and on C1D8 (predose and at the end of the infusion).
- f: Electrocardiogram (ECG) will be performed at Screening, C1D1, C1D8, and at any unscheduled visits as clinically indicated. ECGs obtained at C1D1 and C1D8 should be performed just prior to and immediately after receiving the eribulin mesylate infusion.

- g: Hematology laboratory assessment must be reviewed prior to every eribulin mesylate administration. Cycle 1 Day 1 hematology assessments may be performed within 3 days prior to the scheduled visit. Subsequent hematology assessments may be performed within 24 hours before the scheduled visit.

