9.5.4.3.2 REPORTING OF STUDY-SPECIFIC EVENTS/EVENTS OF CLINICAL INTEREST

Study-specific events (Events of Clinical Interest [ECIs]) should always be considered as serious important medical events and be entered on the Adverse Event CRF and reported using the procedures detailed in Reporting of Serious Adverse Events ([Section 9.5.4.1](#)), even if the study-specific event does not meet other serious criteria.

Events of clinical interest for this study include: an elevated AST or ALT lab value that is greater than or equal to $3 \times$ ULN and an elevated total bilirubin lab value that is greater than or equal to $2 \times$ ULN and, at the same time, an alkaline phosphatase lab value that is less than $2 \times$ ULN, as determined by way of protocol-specified laboratory testing or unscheduled laboratory testing.*

*Note: These criteria are based upon available regulatory guidance documents. The purpose of the criteria is to specify a threshold of abnormal hepatic tests that may require an

additional evaluation for an underlying etiology. The study site guidance for assessment and follow up of these criteria can be found in the Investigator Study File Binder (or equivalent).

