9.7.1.8.2 ADVERSE EVENTS

Dose-limiting toxicity in the first cycle will be used to determine the RP2D. The DLT rate will be summarized descriptively at each combination dose level in the DLT evaluable set. Subsequent dose-limiting toxicity will be reported and summarized as well.

The AE verbatim descriptions (investigator terms from the CRF) will be classified into standardized medical terminology using Medical Dictionary for Regulatory Activities (MedDRA). Adverse events will be coded to the MedDRA (Version 17 or higher) lower level term (LLT) closest to the verbatim term. The linked MedDRA preferred term (PT) and primary system organ class (SOC) are also captured in the database.

A TEAE is defined as an AE that had an onset date, or a worsening in severity from baseline (pretreatment), on or after the first dose of study drug administration up to 30 days (90 days for SAEs and/or ECIs) following study drug discontinuation.

Only those AEs that were treatment emergent will be included in summary tables. All AEs, treatment-emergent or otherwise, will be presented in subject data listings.

The incidence of TEAEs will be reported as the number (percentage) of subjects with TEAEs by SOC and PT. A subject will be counted only once within an SOC and PT, even if the subject experienced more than 1 TEAE within a specific SOC and PT. The number (percentage) of subjects with TEAEs will also be summarized by CTCAE v4.03.

The number (percentage) of subjects with TEAEs will also be summarized by relationship to each study drug. Treatment-related TEAEs include those events considered by the investigator to be possibly or probably related to study treatment or with missing assessment of the causal relationship. Serious adverse events (SAEs), deaths, TEAE with Grade 3 or above, and TEAEs that led to treatment discontinuation, dose reduction or dose interruption will be summarized.

Adverse events of clinical interest, described in [Section 9.5.4.3.2](#), will be summarized descriptively. Details will be provided in the SAP.

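### SAP 6.6.3 identifies the hepatic event of clinical interest, a concurrent laboratory composite, by four adverse-event preferred terms, with no rule that applies the definition; which records carry the 90-day window is also unclear

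*SAP*

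**What the plan says.** Protocol 9.5.4.3.2 defines the ECI by three laboratory conditions: AST or ALT ≥3×ULN, total bilirubin ≥2×ULN, "and, at the same time, an alkaline phosphatase lab value that is less than" 2×ULN. Scheduled and unscheduled tests both count. Such events "should always be considered as serious important medical events" and go on the adverse event (AE) form and through serious adverse event (SAE) reporting. Protocol 9.7.1.8.2 says that these events "will be summarized descriptively. Details will be provided in the SAP".

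SAP 6.6.3 repeats the definition and continues: "We used the following AE PT terms to identify ECI above". Four preferred terms (PTs) follow: ALT increased, AST increased, blood bilirubin increased and blood alkaline phosphatase increased. The same section extends the treatment-emergent window from 30 days after the last dose to "90 days for SAEs and /or events of clinical interest".

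SAP 6.6.4 uses the label ECI differently. It applies it primarily to potential immune-related events, together with eribulin-specific events such as neuropathy and neutropenia. It plans summaries by standardized MedDRA query, PT and grade. SAP 6.6.5 plans by-visit summaries and shift tables to worst grade, one parameter at a time. ECI listings, derivation rules and table shells are in separate files (SAP 6.6.4, 9 and 11) that are not part of the public documents.

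**The concern.** The definition is a conjunction of numeric limits at one time, determined from laboratory results. A preferred term carries no multiple of ULN, no link to another analyte and no upper limit. One of the four terms is a raised-ALP term, although the definition caps ALP.

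Errors are possible in both directions. A subject with an isolated ALT rise has a listed term but not the event. Conversely, Protocol 9.5.1.6.1 says "Abnormal laboratory values should not be listed as separate AEs if they are considered to be part of the clinical syndrome" being reported, so a subject who meets the definition may be recorded under a liver diagnosis and have none of the four terms. At stake is whether the reported ECI figure is a count of the liver event that the protocol defined and left to the SAP to summarize.

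There is also a question of scope. The 90-day window is attached to a label that SAP 6.6.3 and 6.6.4 use for different sets of events, and the protocol passages on how long ECIs are collected and followed disagree.

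**Working it through.** The plan gives no figure to reproduce. The check is logical, with inputs from SAP 6.6.3 (definition and terms), Protocol Appendix 2 (grades) and Protocol 9.5.1.6.1 (recording).

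**1. Missing combination rule.** Four terms, each present or absent, give 2⁴ − 1 = 15 non-empty patterns.
- Any of the four terms: 15 patterns flagged.
- (ALT or AST) and bilirubin: 3 × 1 × 2 = 6 patterns, of which 3 have no ALP term.
- All four terms: 1 pattern, which requires ALP increased.

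The set of subjects flagged therefore depends on a rule that the SAP does not state.

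**2. Thresholds, timing and ceiling.** These are constructed cases in multiples of ULN. In cases 1 to 5, assume that each rise was recorded as an AE.

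| Case | ALT | Bilirubin | ALP | Meets definition? | Listed terms |
|---|---|---|---|---|---|
| 1 | 4 | 2.5 | 1.5 | Yes | ALT, bilirubin, ALP |
| 2 | 4 | 1.8 | 1.5 | No (1.8 < 2) | same |
| 3 | 4 | 2.5 | 2.5 | No (2.5 ≥ 2) | same |
| 4 | 4 | 2.5, at another visit | 1.5 | No (not concurrent) | same |
| 5 | 4 | normal | normal | No | ALT |
| 6 | 4 | 2.5 | 0.8 | Yes, recorded only as a liver diagnosis | none |

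Cases 1 to 4 have the same terms. They also have the same worst grades in Appendix 2: ALT Grade 2 (>3.0–5.0), bilirubin Grade 2 (>1.5–3.0) and ALP Grade 1 (>ULN–3.0). Both 2×ULN limits fall inside a grade, and a worst grade carries no date. PT plus grade therefore cannot separate case 1 from cases 2 to 4. Any rule that starts from the four terms misses case 6.

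**3. Baseline.** Protocol 9.3.1 allows ALT and AST up to 5× "ULN if subject has liver metastases". Since 5 ≥ 3, the transaminase condition can already hold at entry. Bilirubin is capped at 1.5×ULN and 1.5 < 2, so the full composite cannot. A laboratory flag therefore needs a stated rule for treatment emergence.

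**4. Time windows for ECIs, side by side.**
- Collection: 30 days in Protocol 9.5.1.6.1; 90 days in 9.5.4.1.
- Follow-up: 30 days in the Synopsis (Safety) and 9.5.1.6.1; 90 days in the Synopsis (Study Design), 9.1, 9.1.3, 9.5.1.3 and Table 8 footnotes a and o; to resolution or stabilization in the Synopsis (Safety) and 9.5.4.1.
- Treatment-emergent window: 90 days in Protocol 9.7.1.8.2 and SAP 6.6.3.
- The 30-day limit after new anticancer therapy is stated in some of these places, but not in the Synopsis (Study Design), 9.1 or footnote o.

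**The case against.** The best defence is that the list only selects candidate records and that the definition just above it is then applied. The ALP term makes sense only on that reading. It would remove the false flags in cases 2 to 5. But the second step is not in the text, and case 6 would still be missed because selection depends on a listed term.

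A second defence is that the list may serve to tag AE records for the 90-day window, which a subject-level flag would not do. This stands in part: if the terms stop identifying the ECI, the SAP must say which records carry that window.

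Third, other routes may capture these cases. ECIs are always serious, so site-recognised cases should appear in the SAE table and listing, and seriousness helps to separate case 1 from cases 2 to 4. A liver diagnosis might also enter the query-based summary in SAP 6.6.4. Not every rise becomes an AE, so the constructed cases show what is possible, not what is frequent. All this limits the harm, but none of it gives a count of the composite.

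Fourth, the separate files may hold a derivation. That is possible. The claim here concerns the SAP text only.

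**Conclusion.** The point holds for the SAP text. The stated identifier does not implement the stated definition, and no display described there counts subjects who meet it. The change should be made, but the effect is limited to descriptive safety reporting; the response-rate analyses are untouched. The conclusion assumes that no separate file supplies the missing rule.

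A reader might infer more than the documents support:
- *That ECI counts will be inflated, or that liver cases will be lost.* Errors can go either way, no event rates are given, and recognised cases should still be reported as SAEs.
- *That the post-treatment sampling gap measures the defect.* "End of Treatment assessments for all subjects will be collected within 30 days of the last dose of study drug", so a laboratory flag has little scheduled data late in a 90-day window. That is a limit of the remedy, not the size of the problem.
- *That the 30-versus-90-day conflict disappears once new anticancer therapy starts.* Several 90-day passages state no such exception, and following to resolution is not bounded at 30 days.
- *That immune-related events should lose the 90-day window.* SAP 6.6.4 calls them the primary ECIs, and Protocol 9.4.1.2 says that they may arise months after the last dose. The scope is for the sponsor to decide and state.

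**What to change.** In SAP 6.6.3:
- Derive a subject-level ECI flag from all scheduled and unscheduled ALT, AST, total bilirubin and ALP results, using the thresholds already given.
- Before database lock, define what counts as simultaneous and what counts as treatment-emergent relative to baseline.
- Reconcile the flag with site-reported ECIs and SAEs, which also cover days after the last scheduled chemistry sample. Report n (%) with a listing that shows whether each case came from the laboratory flag, the site report or both.
- Stop using the four terms as the ECI identifier. If a separate file already holds an adequate derivation, cite it instead.
- State which AE records carry the 90-day ECI window, and whether the events in SAP 6.6.4 are among them.

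In the protocol, reconcile the passages on ECI collection and follow-up with one another, with the 90-day treatment-emergent window and with the always-serious statement. Say whether the new-therapy exception applies throughout. No particular window is proposed here.

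The cost is SAP wording, one derived flag, one reconciliation, one listing and a protocol clarification. No new data collection is needed, but after End of Treatment the count depends on unscheduled results or site reports having been entered.

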6.6.4 Treatment-Emergent Adverse Events of Special Interest

Potential immune-related adverse events (irAE) are the primary events of clinical interest (ECIs) in addition to the adverse event specific to eribulin (peripheral neuropathy and neutropenia, etc). The listings of ECI potentially related to Pembrolizumab, Eribulin or both are documented in separate files.

Standardized MedDRA Queries (SMQ) of treatment-emergent ECI will be summarized by MedDRA preferred term and CTCAE grade.

6.6.5 Laboratory Values

Clinical laboratory tests to be performed, including hematology, chemistry and urinalysis are summarized in [Table 1](#).

Laboratory results will be standardized and summarized using Système International (SI) units, as appropriate. For all quantitative parameters listed in [Table 1](#), the actual value and the change from baseline to each postbaseline visit and to off treatment visit (end of treatment defined as the last value within 30 days of the last study dose) will be summarized by visit using descriptive statistics.

Laboratory parameters will be categorized according to CTCAE v4.03 grades. Shift tables of laboratory values by CTCAE grade from baseline to worst grade will be provided. Percentages will be based on the number of subjects with non-missing baseline and relevant postbaseline results.

Table 1. Clinical Laboratory Tests

Category	Parameters
Hematology	Hematocrit, hemoglobin, platelets, RBC count, and WBC count with differential (bands, basophils, eosinophils, lymphocytes, monocytes, neutrophils), ANC
Clinical Chemistry	
Electrolytes	Sodium, potassium, chloride, calcium, magnesium
Liver Function Tests	ALT, AST, alkaline phosphatase, total bilirubin, direct bilirubin
Renal Function	BUN, serum creatinine
Thyroid Function	TSH, T4 ^a
Serum pregnancy	Serum β -hCG
Other	LDH, total protein, glucose (fasting ^b)
Urinalysis	Glucose, ketones, pH, protein, RBCs, WBCs, specific gravity

ALT = alanine aminotransferase, ANC = absolute neutrophil count, AST = aspartate aminotransferase, β -hCG = beta-human chorionic gonadotropin, BUN = blood urea nitrogen, LDH = lactate dehydrogenase, RBC = red blood cells, T4 = thyroxine, TSH = thyroid stimulating hormone, WBC = white blood cells

a: Thyroid function will be assessed at the Screening Visit and then every 2 cycles (starting at C2) throughout the study.

b: Fasting glucose at Screen, only

